## 2. LAY SUMMARY: The Rhode Island Prescription and Illicit Drug Study (RAPIDS)

This study will test the efficacy of a novel drug-checking intervention to prevent fatal and non-fatal overdose among people who use drugs (PWUD), who are 18-65 years old at the time of enrollment. We will evaluate whether the incorporation of rapid fentanyl testing into a theory-driven overdose education and prevention intervention reduces rates of overdose compared to standard overdose education and naloxone distribution. Results from this study will significantly improve public health efforts to address the fentanyl overdose epidemic and reduce harms associated with exposure to drugs contaminated with fentanyl. This is a full clinical trial, building on our previously approved fentanyl-test-strip pilot study (2016-2017), the results of which have recently been published.

- 1Krieger MS, Yedinak JL, Buxton JA, et al. High willingness to use rapid fentanyl test strips among young adults who use drugs. *Harm Reduct J* 2018;15(1):7.
- 2 Krieger MS, Goedel WC, Buxton JA, Lysyshyn M, Bernstein E, Sherman SG, Rich JD, Hadland SE, Green TC, [name] BDL. Use of rapid fentanyl test strips among young adults who use drugs. *Int J Drug Policy*.

# **THE RAPIDS CLINICAL TRIAL:**

## **Appendix B: RAPIDS Protocol**

### **PROTOCOL NARRATIVE Aims & Methodology**

#### **3.1a. Specific Aims & Methodology**

In light of the urgent need for research on novel interventions to prevent illicitly-manufactured fentanyl (IMF) exposure and overdose, we will determine whether a brief, theory-driven overdose prevention intervention incorporating “take home” rapid fentanyl testing decreases overdose among adults. We will enroll up to 550 PWUD at risk of overdose in a randomized trial, hereby referred to as the **Rhode Island Prescription and Illicit Drug Study (RAPIDS)**.

In **Aim 1**, we will assess the efficacy of the RAPIDS intervention on preventing overdose among PWUD. In **Aim 2**, we will determine whether the intervention effects are mediated through our model constructs, including knowledge, motivation, behavioral skills, and self-efficacy to use the fentanyl test strips and engage in overdose risk reduction practices. In **Aim 3**, we will determine whether there is heterogeneity of treatment effect related to key participant characteristics, including age, baseline motivations to use the test strips, as well as type and frequency of drug use. By determining the sub-groups for whom intervention efficacy is highest, these findings will guide optimal implementation of this brief intervention to reduce overdose among PWUD.

Eligibility criteria include reported use of heroin, illicit stimulants, counterfeit prescription pills, or injection drug use in the past 30 days, regardless of treatment status (see **Table 1**). An overview of the study design is included in section **3.1.d** below. Participants will be randomized 1:1 to receive the RAPIDS intervention or the attention-matched control condition.

Experimental arm participants will receive the RAPIDS intervention, which includes education about the dangers of IMF, motivational interviewing to increase willingness to use fentanyl test strips and engage in overdose risk reduction behaviors, hands-on training to use the test strips, and opportunities to plan and role- play how to implement overdose risk reduction behaviors upon receipt of a positive or negative test result. In addition, intervention participants will receive ten test strips for personal use. Motivational interviewing “booster” sessions will occur at 1, 2, and 3 months post-randomization, with additional test strips provided on an as needed basis. In the attention-matched control arm, participants will receive standardized overdose education and naloxone distribution (OEND) training, with attention-control visits at 1, 2, and 3 months.

Participants in both arms will receive a naloxone kit after completion of the first session, and information regarding where to obtain additional naloxone at subsequent visits. Follow-up interviews will occur at 6 and 12 months. The primary endpoint will be the rate of self- reported overdose over the follow-up period. Secondary endpoints (e.g., accidental overdose death and suspected EMS runs for overdose) will be ascertained by data linkage to statewide overdose surveillance databases maintained by the research team. Consistent with recruitment rates in our prior studies, we aim to enroll 20 participants per month starting in Year 1 until target

enrollment is reached.

During the baseline visit, participants in both the experimental and control arms will be given a naloxone kit that includes two doses of intranasal naloxone along with a wallet card with information about fentanyl and the educational flyer in a discreet pouch or bag. At all other assessment visits participants will be referred to community locations for no-cost or low-cost naloxone access. We have created a flyer (see **Attachment B**) that provides specific information about locations where naloxone can be obtained, as well as a link to a page that contains this information on [www.PreventOverdoseRI.org](http://www.PreventOverdoseRI.org). In Rhode Island, naloxone is available via pharmacies and community organizations to anyone in the state via standing order authorized by [name] (RAPIDS co-investigator). Additionally, all participants will be asked to provide a urine sample for a 12-drug panel rapid urine screen plus fentanyl rapid urine screen (one sample) at each study visit. The urine screens are not meant to determine a participant's eligibility based on their self-reported drug use. The urine screens will measure fentanyl and other recent drug exposure among participants to determine if there was unintentional exposure to fentanyl. Once a urine screen is completed, the sample will be disposed of immediately. Finally, participants will be asked to provide dried blood spots at three study visits (i.e., baseline, 6 months and 12 months) to confirm results from urine screening in the 12-drug panel above, in addition to detection of novel synthetic opioid and other psychoactive substances. Testing of dried blood spots will be undertaken routinely throughout and at the end of the study, and will not be used to determine a participant's eligibility. After the samples have been analysed for the study endpoints as specified in the protocol, remaining samples will be stored for use in future Institutional Review Board approved substance use and infectious disease (e.g., HIV, hepatitis C, and COVID-19) related research. Additional consent will not be sought for this storage and future use.

**Table 1. RAPIDS Clinical Trial Summary**

Brown Investigative Team	PI: [name] Associate Professor, Department of Epidemiology  Co-I: [name] Associate Professor, Behavioral and Social Sciences
Total Enrollment	n = 550 (maximum for all activities)
Proposed Timeline	Recruitment begins 12/01/2019 and continues until target enrollment is reached
Clinicaltrials.gov status	Approved: NCT043772238
Intervention Name	The RAPIDS Intervention (2 arm study)
Inclusion/Exclusion Criteria	
 
• 18 to 65 years of age;
 
• reside in Rhode Island;
 
• are able to complete interviews in English;
 
• self-report past 30 day use of heroin, illicit stimulants (e.g., powder cocaine, crack, methamphetamine), counterfeit prescription pills, or injection drugs, regardless of treatment status; and
 
• Participants who refuse consent to participate, are unable to provide informed consent due to altered mental status, or who cannot adequately hear and/or comprehend either consent process, will not be enrolled.
 
• Participants who exclusively misuse medications obtained from a physician or diverse of someone else's prescription will not be enrolled
 

Number of study visits	7 total over 12 months Baseline (60 minutes) + follow-ups (60 minutes) (Follow-ups at 1mo, 2mo, 3mo, 6 mo, 12mo)
Compensation	\$35 for the first and last two visits, and \$25 for the three intermediate visits, and an opportunity to earn an additional \$5 at the visit at 3,6, and 12 months, up to \$195 total if participant attends all sessions

### **3.1 b. Detailed description of the RAPIDS intervention (Experimental Arm)**

The intervention is based on two behavioral frameworks: the **Information-Motivation-Behavior (IMB) model**, and the **self-efficacy model** as applied to addictive behaviors.

**The RAPIDS intervention provides** (see also **Figure 4** from grant proposal):

[figure not shown]
1. education about the dangers of IMF and how to prevent overdose (information);
2. motivational interviewing to encourage risk reduction behaviors (motivation) and to assess and improve participants' confidence in implementing these behaviors (self

efficacy);

3. hands-on training demonstrating how to use and interpret fentanyl test strips (behavioral skills), including opportunities to practice using the test strips; and
4. provision of BTNX Rapid Fentanyl test strips (see **Attachment B**) for personal harm reduction use.

Specifically, the intervention will directly increase engagement in the target overdose risk reduction behaviors, and indirectly through fentanyl test strip utilization. In other words, **we hypothesize that fentanyl test strip utilization is an important, but not exclusive, behavioral mediator through which the intervention will prevent overdose among PWUD.**

**Figure 4: RAPIDS Intervention Conceptual Model**

#### **Survey Assessment Description (for complete survey instrument see **Attachment A**):**

**Information:** Participants will be assessed on their knowledge of fentanyl and overdose prevention strategies with multi-item scales (e.g., agreement with statements such as, “Someone is more likely to overdose when using fentanyl-laced drugs than when using drugs that aren’t laced with fentanyl,” and, “Do you know where you buy or get Narcan™, a medication sometimes called naloxone?”).

**Motivation:** Participants will be assessed on their motivation to use the rapid fentanyl tests (e.g., agreement with a statement reading, “I am concerned about my drugs being contaminated with fentanyl”) and engage in overdose risk reduction behaviors (e.g., agreement with a statement reading, “I am confident that I can ask someone to check on me after I use drugs and call 911 if they think I am overdosing”).

**Behavioral Skills:** Participants will be assessed on their behavioral skills related to use of the rapid fentanyl tests (e.g., “I feel confident in my ability to use the test strips to detect if there is fentanyl in my drugs”) and engagement in overdose risk reduction behaviors (e.g., “What do you do to avoid an accidental overdose?” and, “Have you ever given Narcan/naloxone to someone who you thought was overdosing?”).

**Self-Efficacy:** Questions about harm reduction self-efficacy will be used to assess participants' confidence to employ specific health-preserving skills in different types of high-risk situations

 [https://www.btnx.com/files/BTNX\\_Fentanyl\\_Strips\\_Harm\\_Reduction\\_Brochure.PDF](https://www.btnx.com/files/BTNX_Fentanyl_Strips_Harm_Reduction_Brochure.PDF)

(i.e., when experiencing withdrawal, when feeling depressed, when feeling social pressure to use drugs in a less safe manner). This scale has shown good internal consistency and construct and discriminant validity.

**Behavioral Outcomes:** Participants in the intervention arm will be asked a series of questions regarding fentanyl test strip utilization at all follow-up assessments. These questions were used successfully in our pilot study, and include items such as, “Of the 10 tests we gave you, how many tests did you use?” and, “What did you do when you found out your drugs were laced with fentanyl?” As an additional measure of test strip utilization, participants will be asked to return unused tests to the study office. We will also assess motivations for using the test strips, including a desire to avoid IMF-contaminated drugs or purposely identifying fentanyl.

At each time point, participants will be asked about the practices they engage in to avoid accidental overdose. Strategies to avoid overdose include the target overdose risk reduction behaviors:

1. discarding IMF-contaminated drugs,
2. not using alone (and staggering drug use with another person who is able to administer naloxone and call 911 in the event of an overdose), and
3. keeping naloxone nearby.

We will also assess other harm reduction practices, including taking a “tester” or lower initial dose, avoiding injection drug use, and purchasing drugs from a consistent source.

**Standard of Care (Attention-Matched Control Arm).** Existing research suggests that training people who are at risk for overdose and their peers on how to respond when witnessing an overdose is a feasible and effective strategy for preventing overdose death. Given that this represents current overdose prevention practice, participants in the control arm will receive the standardized OEND training that occurs in Rhode Island. This program is based on the common components of many community-based overdose prevention interventions in the US, and includes information on risk factors for overdose, recognizing an overdose, performing rescue breaths, administering naloxone, and recommendations to call 911. **To ensure equivalent attention to the RAPIDS arm, control arm participants will return for retention visits at 1, 2, and 3 months,** and will answer a series of questions regarding substance use and overdose risk behaviors.

**Potential Moderators/Other Key Measures:** The RAPIDS survey instrument will contain additional behavioral, psychological, and clinical assessments asked of everyone in the study. Many of these questions have been piloted successfully in our prior research.

Consideration of Sex, Biological Variables, and Other Sociodemographic Characteristics: Participants will report their age, sex at birth, current gender identity, sexual orientation, race, ethnicity, educational attainment, employment status, and recent and lifetime experiences of housing instability and homelessness, involvement

with the criminal justice system, and participation in sex work.

Substance Use Experiences: Participants will report on recent and lifetime substance use patterns (i.e., age at first use, frequency of use, polysubstance use, binge use, social context of use, route of administration), and perceptions towards fentanyl (i.e., intentional use of fentanyl, suspected exposure to fentanyl-contaminated drugs). The questionnaire will also incorporate a number of standardized instruments, including the Addiction Severity-Index Lite (drug and alcohol section), and the Short Opiate Withdrawal Scale (SOWS).

Healthcare Utilization: Participants will report on health insurance status; prior mental health diagnoses, past treatment experiences, use of medications (buprenorphine, naltrexone, or methadone), and barriers to substance abuse treatment. We will administer a modified version of the Circumstances, Motivation, and Readiness (CMR) scale, which has been used to assess motivation to engage in substance use treatment.

**Rapid Urine Screen Tests, Dried Blood Spot and Survey Administration Procedures:**

Participants will check in at the Brown University School of Public Health Lobby - [name] and be escorted to a private interview room by *Research Assistant A*. All consenting procedures and surveys/interviews will be conducted in the private interview room. Each visit will last 60 minutes.

**Two trained *Interventionist Research Assistants* (RAs) will manage the visits to [name]:**

- The first RA, *Research Assistant A*, will be responsible for the informed consent protocol and conducting the survey assessment with the participant. They will also be responsible for administering the RAPIDS intervention for participants randomized to the intervention, which includes the provision of 10 BTNX Rapid Test Strips for take-home, personal harm reduction use.
- The second RA, *Research Assistant B*, will be responsible for conducting the rapid drug screen with the participant. Participants will provide a urine sample for a 12-drug panel and fentanyl baseline urine screen.
- *Research Assistant B* will record the results of the urine screen using the participant number identifier; results will not be shared with the participant.
- *Research Assistant B* will be responsible for the collection and storage of dried blood spots using capillary finger-stick methods for the purposes of toxicology screening and future use related to substance use and infectious diseases, results of which will not be shared with the participant. *Research Assistant B* will complete required specimen collection logs detailing the date and quantity of dried blood spot specimens collected.

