Blinding: Staff conducting the baseline and follow- up assessments will be blinded to intervention assignment until completion of the STUDY ENROLLMENT INFORMED CONSENT FORM at the Baseline visit. Intervention allocations will be maintained in REDCap by authorized users only, such as the study Statistician, and revealed only through REDCap by prompts during the baseline survey visit and post-baseline visits.

Retention: To maximize retention, we will employ retention strategies that are effective with PWUD.

For example, we have found that text messages are the preferred mode of communication: over 95% of participants in our pilot study owned a cell phone and used it daily. We have included study cell phones in the budget so project staff can text participants at least monthly to update contact information. Additional retention strategies to be employed include: (1) maintaining a tracking database of contact information (e.g., phone numbers, email addresses, social media handles, physical addresses for sending appointment reminder postcards); (2) conducting regular outreach in areas that participants are known to frequent; (3) providing honoraria for all study visits; (4) providing free parking to participants visiting the study office by validating garage parking passes; (5) searching the public RI Department of Corrections database to determine if a participant is incarcerated for a period of longer than 90 days, at which point they will be withdrawn from the study. These strategies were used effectively in our RAPIDS pilot study, resulting in a 90% follow-up rate.

**3.1 e How confidentiality of data will be maintained (where data is kept, who has access to it, and how it is kept secure).** The Principal Investigator, [name] is ultimately responsible for data safety and monitoring of the study. This process will be monitored on a weekly basis by his team, including the Project Director, Data Analyst, and Senior Research Assistant, with quarterly updates to the entire team of Co-Investigators. The project team will be responsible for ensuring that all policies and processes outlined in the Data Use Agreement (with Rhode Island Department of Health, **Attachment E**) are followed accordingly, and that data are

 <http://cri.uchicago.edu/wp-content/uploads/2015/12/REDCap-Randomization-Module.pdf>

transferred and shared on the agreed-upon timeline.

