### **ARM ASSIGNMENT [PIPE FROM SCREENER, RA SEES ARM ASSIGNMENT]**

- **ARM 1 (Control)**
- **ARM 2 (Experimental)**

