**F13. Since your last visit, have you accidentally overdosed? [odsincevist]**

- Yes
- No
- DK/R

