## **SECTION G: RAPIDS INTERVENTION (EXPERIMENTAL ARM ONLY)**

## **Break for intervention booster session:** *Pipe in response from F12, F28, and F29.*

## **PIPE**

**G.0. Now I would like to talk to you about how you are doing with the change goals that we talked about the last time you were here.**

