- Each staff person will be limited to no more than 3 participant visits per day during Stage II of Brown University reopening. This will ensure that there will be ample time to disinfect the study space between visits and will minimize the number of interactions that the research staff have in the course of a day. We will re-evaluate the number of participant interactions in a day as the university transitions to different stages of re-opening.
- In order to adhere to Stage II building density guidelines, the portion of the study visit that will take place in person will occur in room 259. This will be reevaluated as Brown University moves to other stages of reopening.

Additional procedures for participant encounters/sessions:

- Staff will ensure there are sufficient cleaning supplies and personal protective equipment on-site at all times. Cleaning equipment will be stored in room 256.
- Staff will disinfect their work space upon entering the building and upon completion of their work day.
- At all times, participants will be seated more than 6ft apart from the research staff.
- Staff will conduct a health pre-screening with research participants prior to their study visits.
- Participants will enter and exit [name] through the main entrance.
- Participants will be asked to use hand sanitizer immediately upon entering the building or will need to wash their hands when they arrive at the second floor. If the participant does not arrive wearing a mask, the participant will need to wash their hands or use hand sanitizer immediately after putting their mask on.
- Research staff will ask all questions out loud and will do all data entry for participants.
- All consent forms will be completed electronically.
- All surfaces will be disinfected after each participant visit. Additionally, all surfaces will be disinfected before the first visit and at the completion of the final study visit each day.
- Signs will be posted reminding participants of how to properly wear their masks and reminding them to wash their hands thoroughly after their visits.

Additional procedures for urine screening:

- There will be one dedicated restroom for participants to use for urine screens. No other staff or participants are allowed to use that restroom.
- Protective equipment, such as masks and gloves, will be worn at all times during urine drug screening, in accordance with the prior-approved protocols.

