There are three major assessment points: baseline, acute outcome (6 months post-randomization), and longer-term outcomes measured at 12 months. At baseline, after reviewing the study protocols and undergoing informed consent, all participants will complete an assessment battery and will then be randomized to one of the two study conditions. At all assessment visits, we will use computer-assisted personal interviewing (CAPI) to conduct participant interviews, which will include a computer-assisted self-interview (CASI) component for the collection of sensitive or stigmatizing information (e.g., injection drug use).

---

 [https://cdn.ymaws.com/www.cste.org/resource/resmgr/ps/ps2022/Recommendations for EMS NFOO.pdf](https://cdn.ymaws.com/www.cste.org/resource/resmgr/ps/ps2022/Recommendations%20for%20EMS%20NFOO.pdf)

 <https://health.ri.gov/data/hospitalization/discharge/>

Stronghold computing environment: We will obtain a central storage service hosted by Brown University's Computing & Information Services (CIS) Stronghold project. Stronghold is a HIPAA-aligned (Health Insurance Portability and Accountability Act), secure computing environment developed for housing, sharing, and analyzing sensitive data. The project's Biostatistician will oversee the database architecture, dataset storage, and all input/output (i.e., RIDOH data transfer) regulations. Stronghold is a highly secure computer and storage Windows-exclusive environment for research needs that involve very sensitive data needing special handling, data usage agreements, etc. See section F1 (Trial Safety) for additional information about Stronghold security.

All Stronghold users must:

- Be approved by the Principal Investigator (PI), authorized in writing to Brown University Computing &
- Information Services (CIS);
- Complete appropriate training for working with sensitive data (e.g. CITI training);
- Be in compliance with all relevant Institutional Review Board protocols;
- Be in compliance with any data use agreements or other agreements governing the use of the data stored on Stronghold; and
- Complete an on-boarding process led by the PI or Senior Research Assistant, which includes a review of data security protocols and a guided walkthrough of accessing the Stronghold virtual environment.

Data Transfers – there are select methods to import data, including but not limited to:

- Select Rhode Island state agencies and other offices using a secure VPN tunnel

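### At follow-up, the self-reported overdose items are collected by a staff role that also delivers the intervention and sees the arm, and nothing assigns those items to self-interview.

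*Protocol*

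**What the plan says.** **Who asks.** Protocol section 3.1b makes one role, Research Assistant A, responsible for "conducting the survey assessment with the participant. They will also be responsible for administering the RAPIDS intervention for participants randomized to the intervention". Research Assistant B runs the urine screen and blood spots. Both are described as interventionist assistants.

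**Who knows the arm.** Under Blinding in section 3.1d, staff who conduct baseline and follow-up assessments "will be blinded to intervention assignment until completion of the STUDY ENROLLMENT INFORMED CONSENT FORM at the Baseline visit". The opening fields of the follow-up form in Attachment A carry the instruction "PIPE FROM SCREENER, RA SEES ARM ASSIGNMENT".

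**What is asked.** In follow-up Section F, an interviewer prompt defines accidental overdose, and F13 then asks "Since your last visit, have you accidentally overdosed". F14 to F16 cover recency, symptoms and number. Section G, for the experimental arm only, comes next on the same form. It draws on answers from Section F and opens with "Now I would like to talk to you about how you are doing with the change goals". Section H, for controls, holds test-strip questions and no coaching.

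**How it is asked.** SAP section 1 promises a "computer-assisted self-interview (CASI) component for the collection of sensitive or stigmatizing information" at all assessment visits, with injection drug use as its example. Section C1 of the Data and Safety Monitoring Plan also relies on CASI. The Reopening Plan says "Research staff will ask all questions out loud and will do all data entry for participants".

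**What counts.** The Monitoring Plan's primary outcome is the rate of self-reported overdose. The SAP's is time to first nonfatal overdose from self-report at months 6 and/or 12, EMS records or emergency department (ED) records. Boosters are scheduled at months 1, 2 and 3.

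**The concern.** Participants cannot be blinded, so the quality of a self-reported outcome depends on how neutral the setting is. Here the intervention arm has set personal overdose-prevention goals with staff in an interventionist role, and reporting an overdose means reporting a setback on those goals to that same role. Controls have had overdose education and matched visits, but no goal-based coaching.

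If the arms differ in readiness to disclose, the difference enters the primary comparison as if it were a treatment effect. Under-reporting in the intervention arm would look like efficacy; fuller reporting there would hide a real benefit. CASI is the standard protection and the plan invokes it, but does not tie it to the items that define the endpoint.

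**Working it through.** **Inputs, all from SAP section 6 unless stated**
- Control risk 20% over 12 months; target 50% reduction, so 10%.
- 250 per arm enrolled at 80% retention, so 200 per arm. Two-sided 0.05 (SAP section 4).
- 38% of self-reported overdoses assumed to lead to death or EMS attendance.
- q, the extra fraction of self-report-only events withheld in the intervention arm. The documents give no value, so q is an assumption shown as a range.

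**Step 1: reproduce the stated power.** Pooled two-proportion test, 20% against 10%, 200 per arm:
- null SE = √(2 × 0.15 × 0.85 / 200) = 0.0357
- alternative SE = √((0.16 + 0.09) / 200) = 0.0354
- power = Φ((0.10 − 1.96 × 0.0357) / 0.0354) = 0.802

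The SAP's figure of more than 80% reproduces, so the same test is used below.

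**Step 2: share of events resting on self-report alone.** 1 − 0.38 = 0.62.

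**Step 3: apparent risk ratio with no true effect.** For the SAP composite it is 1 − 0.62q. For the Monitoring Plan's self-report outcome it is 1 − q. The chance of a significant result favouring the intervention (nominally 2.5%) uses the Step 1 test with 20% in controls and 20% times the apparent risk ratio in the intervention arm.

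| q (assumed) | Composite: risk ratio | Composite: false benefit | Self-report only: risk ratio | Self-report only: false benefit |
|---|---|---|---|---|
| 20% | 0.88 | 9.3% | 0.80 | 17.9% |
| 30% | 0.81 | 16.0% | 0.70 | 35.8% |
| 50% | 0.69 | 38.0% | 0.50 | 80.2% |

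A simulation of 200,000 trials agreed to within about one percentage point.

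**Step 4: how much withholding gives significance by itself.** Against 40/200 in controls, the test needs 25/200 or fewer, a shortfall of 37.5%. Under the composite that is q = 0.375 / 0.62 ≈ 60%. No q in the table reaches it in expectation; what rises is the false-positive rate.

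**Step 5: allow for attrition.** Records cover everyone who is linked, but self-report covers only those retained. With 80% retention and equal risk among those lost, the self-report-only share of observed events is (0.8 × 0.62) / (0.8 × 0.62 + 0.38) = 0.496 / 0.876 = 0.57. The risk ratios become about 0.89, 0.83 and 0.72.

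**Step 6: the planned checks.** The SAP's concordance check between self-report and records is written for missing self-report. It does not compare reporting by arm. The exploratory comparison of EMS, ED and fatal events is by arm and unaffected by what participants tell staff. At 8% against 4% and 250 per arm, the Step 1 test gives about 47% power. The SAP states at least 80% for its exploratory endpoint; that discrepancy is a separate matter.

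**The case against.** Several stronger readings are tempting, and the documents do not support them.

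- **That participants report to their own coach.** A and B are roles. Nothing says the same individual sees a participant at every visit, although the Reopening Plan brings back only two staff.
- **That coaching and the counted overdose question occur at the same visit.** Boosters are scheduled at months 1 to 3, and SAP self-report counts at months 6 and 12. The single follow-up form carries Section G, but no schedule places coaching at those later visits. Earlier coaching is the mechanism at issue.
- **That CASI was abandoned.** The Reopening Plan is a COVID measure, and section 3.1g says procedures may change. It conflicts with the SAP; it does not prove that self-interview was dropped.
- **That no planned analysis could reveal the problem.** The exploratory records-only comparison could. It is not designated for that purpose and is less powerful.
- **That Research Assistant B is independent.** Both assistants are interventionists, so B may have coached the participant on another day.
- **That the bias must favour the intervention.** Rapport could increase disclosure, controls also receive prevention training, and staff are trained on stigma.

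The 62% is also soft. The SAP applies the 38% to death or EMS attendance, while the Monitoring Plan applies it to death or ED presentation. The composite accepts EMS and ED records, so capture could be higher.

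These points narrow the concern without removing it. The overdose items still have no assigned self-interview and no assessor blind to the arm.

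**Conclusion.** The concern holds as a gap in outcome ascertainment. A role that delivers the intervention and sees the arm collects F13 to F16, coaching was given in one arm only, and the documents disagree on whether such questions are self-completed or asked aloud. The plan shows neither that a bias exists nor which way it would run.

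Under the SAP composite, extra withholding of 20% to 50% in the intervention arm would turn no effect into a risk ratio of about 0.88 to 0.69, or 0.89 to 0.72 after allowing for attrition. This rests on an assumed q, on the 38% as an approximate record-capture rate, and on a 12-month two-proportion calculation in place of the SAP's time-to-event analysis. EMS and ED records dilute the effect but do not remove it. The change is worth making because it is cheap and protects the primary endpoint.

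**What to change.** 1. Assign F13 to F16 explicitly to CASI at every follow-up visit, before any arm-specific content and preferably before the Section C test-strip items, which can reveal the arm.
2. Exempt these items from the Reopening Plan's rule on asking aloud, and reconcile that rule with SAP section 1 and Monitoring Plan section C1.
3. Hide the arm field on the follow-up form until the break for Section G or H.
4. Where a participant cannot read the items, have an assistant who has not coached that participant ask them.
5. Name the EMS, ED and overdose-death comparison in the SAP as the pre-specified sensitivity check for self-report that differs by arm.

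The SAP takes self-reported event dates from SAE reports, so a CASI yes must still lead to that report; the point is that disclosure comes first.

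The cost is form settings, a staff instruction and a routine amendment needing IRB and NIDA approval. No extra staff or visits are needed: two assistants already run each visit, and the Reopening Plan already seats participants at a laptop in a separate room. Some interviewer probing is lost, a reading fallback is needed, and hiding the field only partly masks staff who remember the arm.
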